8.1 Clinical adverse events

In addition to nephrotoxicity and ototoxicity, the MAP chemotherapy regimen is expected to cause substantial toxicity in all patients undergoing treatment for osteosarcoma, including myelosuppression, febrile neutropenia and infection, nausea and vomiting, mucositis, anorexia, weight loss, fatigue, hepatotoxicity, and neurotoxicity.

Clinical adverse events (AEs) related to the research interventions, which are administration of pantoprazole with cisplatin and prolonging the infusion duration of HDMTX, will be monitored throughout this study.

8.2 Adverse Event Reporting

SAEs will be promptly reported to the IRB in accordance with CHOP IRB policies. AEs that are not serious but that might involve risks to subjects will be summarized in narrative or other format and submitted to the IRB at the time of continuing review.

8.3 Definition of an Adverse Event

An adverse event is any untoward medical occurrence in a subject who has received an intervention (drug, biologic, or other intervention). The occurrence does not necessarily have to have a causal relationship with the treatment. An AE can therefore be any unfavorable or unintended sign (including an abnormal laboratory finding, for example), symptom, or disease temporally associated with the use of a medicinal product, whether or not considered related to the medicinal product.

AEs (including SAEs) that are grade ≥ 2 in severity and related to the treatment will be collected in an eCRF in OnCore including CTCAE category, grade, date of onset, duration, attribution (causality), and outcome of the event (resolution).

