6.1.2 Secondary Endpoints

- **Common grade ≥ 2 toxicities** from cisplatin + doxorubicin (other than cisplatin nephrotoxicity and ototoxicity), including myelosuppression, mucositis, nausea and vomiting leading to dehydration requiring IV fluid hydration, peripheral neuropathy, cardiac dysfunction, and treatment delays due to toxicity will be collected and graded according to CTCAE v.4. Similarly, HDMTX-related grade ≥ 2 toxicities (other than nephrotoxicity), including myelosuppression, mucositis, dermatitis, hepatotoxicity and neurotoxicity will be collected and graded. The incidence and severity (grade) of toxicities will be tabulated and compared by treatment arm (with vs. without

pantoprazole for cisplatin + doxorubicin and by infusion duration for HDMTX).

- **Response** to 2 cycles of neoadjuvant chemotherapy will be assessed radiographically and histologically.
 - The volume of the tumor on MRI will be measured pretreatment and pre-operatively (post-cycle 2). The log ratio (Section 5.2) of the two measurements will be derived and compared using a non-parametric analysis for cisplatin with (patients on treatment arms 1 and 3) vs. without (patients on treatment arms 2 and 4) pantoprazole and for HDMTX administered as a 4 h infusion (treatment arms 1 and 2) vs. a 12 h infusion (treatment arms 3 and 4).
 - The tumor specimen that is removed after 2 cycles of neoadjuvant chemotherapy will be evaluated histologically and the percent of the tumor that is necrotic will be estimated from review of multiple sections. The percent necrosis will be compared using a non-parametric analysis for cisplatin with (patients on treatment arms 1 and 3) vs. without (patients on treatment arms 2 and 4) pantoprazole and for HDMTX administered as a 4 h infusion (treatment arms 1 and 2) vs. a 12 h infusion (treatment arms 3 and 4).
- **GFR** estimated from serum creatinine using the modified Schwartz formula will be correlated with GFR estimated from serum cystatin C (Section 1.3.3, the equation also includes serum creatinine and BUN). The presence and amount (normalized to creatinine concentration) of biomarkers of AKI in urine will be correlated with proteinuria, serum creatinine, and change in FEMg.

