7.1 Intravenous Pantoprazole (PROTONIX I.V.)

- **IUPAC Name:** (RS)-6-(Difluoromethoxy)-2-[(3,4-dimethoxypyridin-2-yl)methylsulfinyl]-1H-benzo[d]imidazole
- **Molecular formula & weight:** C₁₆H₁₅F₂N₃O₄S - 383.4 g/mol (Fig 5, chemical structure)
- **Manufacturer:** Pfizer Injectables (Distributed by Wyeth Pharmaceuticals Inc.)
- **Drug supply:** purchased from commercial sources
- **Indications:** gastroesophageal reflux associated with a history of erosive esophagitis and pathological hypersecretory conditions (e.g., Zollinger-Ellison syndrome)
- **Dosage forms and strength:** supplied in a vial containing 40 mg of pantoprazole as a freeze dried powder
- **Storage and Handling:** store vials at 20-25°C (USP controlled room temperature); excursions permitted to 15-30°C.
- **Dosing (Section 3.1.3):** 0.3 mg/kg IV over 15 min immediately prior to each dose of cisplatin as a loading dose followed by 1.3 mg/kg IV infused over 4 h concurrent with each 4 h cisplatin infusion on either Cycles 1 & 2 OR Cycles 3 & 4 depending on the treatment arm. See Section 1.3.8 for the rationale for pantoprazole administration schedule.
- **Compatibility:** the compatibility of the cisplatin and pantoprazole drugs solutions was

Protocol number: CHP12ST051
Amendment number:
Version date: April 2, 2013

tested at UPenn by [name], and at the concentrations used for drug administration, there was no evidence of an interaction – indicating that the pantoprazole solution can be infused into the same intravenous tubing through which the cisplatin is being infused.

- **Clinical pharmacology:** see Section 1.3.5 for pediatric pharmacokinetic data and tolerability of single doses in children
- **Adverse reactions:** reactions reported in clinical trials in adults (n=1473) with GERD at a frequency >2% included headache (12%), diarrhea (8.8%), nausea (7%), abdominal pain (6.2%), vomiting (4.3%), flatulence (3.9%), dizziness (3%), arthralgia (2.8%). The use of PPIs is associated with a moderately increased risk of *C. difficile* colitis.^{113,114}
- **Drug accountability:** a separate drug supply will be purchased for this study using the research funds, and NCI DARFs will be used to track drug supply.
- **IND status:** this pilot study will evaluate pantoprazole for a non-approved indication. The use of pantoprazole in this study meets the five criteria for IND exempt status:

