8.4.1 Relationship of SAE to study drug or other intervention or procedure

The relationship of each SAE to the study intervention will be characterized using one of the following terms in accordance with CHOP IRB Guidelines: definitely, probably, possibly, unlikely or unrelated.

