9.3 Regulatory and ethical considerations

9.3.1 Data safety and monitoring plan

The research team led by the protocol PI will monitor adverse events related to the protocol therapy in real time. The progress of every patient actively receiving treatment on this study will be discussed weekly in the Solid Tumor Team Meeting. An interim analysis to assess the safety of the interventions will be performed after the first 12 patients have completed therapy.

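### The adverse event record holds only events judged related to an undefined treatment, in a trial with no blinding described, which leaves part of the planned toxicity comparison open to differential attribution

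*Combined protocol and SAP*

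**What the plan says.** Section 8.3 first defines an adverse event broadly: "The occurrence does not necessarily have to have a causal relationship with the treatment". It then sets a narrower rule for what is kept: events, SAEs included, that are grade 2 or higher and "related to the treatment will be collected in an eCRF in OnCore". Attribution is one of the fields on that form. Two other sections also speak only of related events, each naming a different object. Section 8.1 monitors "Clinical adverse events (AEs) related to the research interventions", meaning pantoprazole and the longer methotrexate infusion. Section 9.3.1 says "The research team led by the protocol PI will monitor adverse events related to the protocol therapy in real time". For SAEs, section 8.4.1 adds: "The relationship of each SAE to the study intervention will be characterized using one of the following terms", on a five-point scale that ends at unrelated.

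These records feed a planned analysis. Section 6.1.2 states: "The incidence and severity (grade) of toxicities will be tabulated and compared by treatment arm", that is, cisplatin plus doxorubicin with or without pantoprazole, and HDMTX by infusion duration. Section 6.3 has the investigators make the same comparison after 12 patients, without a statistical stopping rule, and lets them drop an intervention whose outcome looks worse to a clinically important degree.

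Section 5.4 separately lists items to be followed by cycle, and section 5.2 makes that list a secondary endpoint. On pantoprazole itself, section 7.1 warns: "The use of PPIs is associated with a moderately increased risk of" C. difficile colitis, and section 9.3.2 repeats the association.

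**The concern.** If an event is entered only once someone calls it related, the recorded incidence is the true incidence multiplied by the chance of that call. No blinding is described. Under section 3.4.1 the study PI assigns the arm, under section 3.1.3 an arm-specific treatment map goes in the clinic chart, and a 4 h infusion is visibly different from a 12 h one. A clinician who knows which condition the patient is in may attribute the same event differently in the two conditions.

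At stake are a secondary comparison and an interim judgement, not the primary biomarker, GFR, FEMg, methotrexate concentration or audiogram results. Two features still make it worth correcting. The harms that the protocol itself associates with proton pump inhibitors have a ready alternative explanation, namely antibiotics for neutropenic fever. And an event that was never entered cannot be re-analysed later.

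**Working it through.** The plan gives no figure on this point to reproduce. The check has two parts: which events depend on the filter, and what unequal attribution would do.

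**1. Which events depend on attribution**

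| Event | Section 5.4, by cycle | Section 6.1.2 | Depends on attribution? |
|---|---|---|---|
| Neutrophil and platelet nadirs, platelet transfusions, admissions for neutropenic fever or infection, peak ALT and bilirubin, grade 3-4 mucositis | Listed, no relatedness condition | Partly overlaps | No, as tracked under 5.4 |
| Delays, missed doses, dose modifications, deaths | Listed, but tied to toxicity | Delays only | Yes |
| Grade 2 mucositis | Not listed | Listed for both drug groups | Yes |
| Dehydrating nausea and vomiting, peripheral neuropathy | Not listed | Listed as arising from cisplatin plus doxorubicin | Yes |
| Dermatitis, neurotoxicity | Not listed | Listed as HDMTX-related | Yes |
| Diarrhoea, C. difficile infection | Not listed | Not listed | Yes, through 8.3 alone |

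Mucositis and myelosuppression appear in 6.1.2 under both drug groups, and both groups are given in the same five-week cycle. Attribution therefore also decides which of the two comparisons such an event enters.

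**2. What unequal attribution would do (illustration)**

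Inputs from section 6.2: 24 patients, with 2 cisplatin courses and 4 HDMTX doses per patient in each condition. That gives 24 × 2 = 48 courses and 24 × 4 = 96 doses per condition. At the 12-patient look it is 12 × 2 = 24 courses per condition. The true incidence *p* and the attribution probabilities *a* are assumptions, because the documents give neither.

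Recorded rate = *p* × *a*. With equal true incidence, the recorded ratio = *a*₁ / *a*₀. For *p* = 0.40:

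| *a* in the two conditions | Recorded rates | Ratio | Events in 48 v 48 courses | Events in 24 v 24 courses (interim) |
|---|---|---|---|---|
| 0.90 v 0.90 | 0.36 v 0.36 | 1.00 | 17.3 v 17.3 | 8.6 v 8.6 |
| 0.95 v 0.85 | 0.38 v 0.34 | 1.12 | 18.2 v 16.3 | 9.1 v 8.2 |
| 0.95 v 0.75 | 0.38 v 0.30 | 1.27 | 18.2 v 14.4 | 9.1 v 7.2 |
| 0.90 v 0.60 | 0.36 v 0.24 | 1.50 | 17.3 v 11.5 | 8.6 v 5.8 |

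Swapping the conditions reverses the direction. The first row shows that a filter applied equally, at whatever level, leaves the ratio at 1.00.

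The plan names no test for these tables. As a yardstick, take a two-sided 0.05 comparison of two proportions with courses treated as independent, which ignores clustering within patients. The chance of a nominally significant result in the biased direction is Φ[(d − 1.96·SE₀)/SE₁], where SE₀ uses the pooled rate. For 0.36 v 0.24 with 48 per condition, SE₀ = √(2 × 0.30 × 0.70/48) = 0.0935 and SE₁ = √((0.36 × 0.64 + 0.24 × 0.76)/48) = 0.0927. The result is Φ[(0.12 − 0.1833)/0.0927] = 0.247, against 0.025 with no bias. For 0.38 v 0.34 it is 0.060. Over the three unequal rows and *p* from 0.20 to 0.60, the range is 0.044 to 0.424 for 48 courses and 0.055 to 0.711 for 96 doses.

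**The case against.** The strongest reply is that the filter has little to act on. Most objective safety data come through section 5.4 without any causality test and are compared by condition in their own right. Section 6.1.2 expressly plans to collect dehydrating nausea and vomiting, neuropathy and dermatitis, attributed to chemotherapy and not to pantoprazole or infusion length. If the treatment in 8.3 means the whole MAP regimen, nearly every expected toxicity qualifies in either condition. The five-point scale in 8.4.1 then keeps a purpose, since an SAE can be caused by MAP yet unrelated to the study intervention. The survey in Appendix 3 asks about diarrhoea, nausea and vomiting. SAEs also have a path to the IRB under 8.2 and 8.4.2. Finally, this is a pilot, and the toxicity comparison is secondary.

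Much of this stands, and it rules out three stronger readings that a reader might infer:

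- **That every toxicity comparison is filtered.** The first row of the item table shows otherwise.
- **That unrelated SAEs are certain to go unrecorded.** 8.3 taken literally says so, but 8.4.1 classifies each SAE and may refer to a narrower object than 8.3 does. The text leaves this unsettled.
- **That the bias is known, or favours the experimental conditions.** Cautious staff could as easily over-attribute events to a novel intervention, and no document gives attribution rates. Nor do the documents name who judges relatedness. That this person knows the allocation is a strong inference, not a stated fact.

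The rest of the reply does not remove the point. The broad reading of the treatment is only one possible reading, and 8.1 points to the narrower one. The 6.1.2 items are themselves defined by attribution. The survey records frequency categories without toxicity grades, and no comparison of it by condition is planned. IRB reports are not the analysis data set, and 8.4.2 opens by confining prompt notice to on-site events that are at once serious, unexpected and linked to research procedures. The 6.1.2 list is introduced as non-exhaustive, so diarrhoea and C. difficile could be added to it, but nothing ensures that they are.

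**Conclusion.** The point holds in a limited form. Section 8.3 makes entry of AEs and SAEs depend on a relatedness judgement whose object is undefined, in a trial with no blinding described. The affected part is the set of graded events found in 6.1.2 but not in 5.4, the 5.4 items that rest on attribution to toxicity, and the PPI harms that neither list names. The interim judgement in 6.3 is affected to the extent that it uses these events.

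Bias follows only if attribution differs between conditions. Its size and direction cannot be estimated from the documents; the ratios of 1.12 to 1.50 above are consequences of assumed inputs. If the treatment means all of MAP, the effect is probably small; if it means the research interventions, the risk is larger. The primary endpoints are untouched. This is a cheap improvement to the safety data, not a flaw in the main analysis.

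**What to change.** 1. In 8.3, enter all SAEs, and all grade 2 or higher events in the 6.1.2 categories plus diarrhoea and C. difficile infection, whatever their judged cause. Keep attribution as a field, and name the object it refers to (MAP, pantoprazole, infusion duration).
2. In 6.1.2 and 6.3, base the comparisons with and without pantoprazole, and of 4 h with 12 h infusions, on all recorded events. Assign each event by its onset in the relevant part of the cycle: from day 1 until the first HDMTX infusion for cisplatin plus doxorubicin, and from that infusion onward for HDMTX. Give attributed events in a supplementary table.
3. Reconcile 8.1, 8.3, 8.4.1 and 8.4.2, so that one statement says which SAEs are recorded, which are classified, and which are reported promptly.

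The cost is a sentence or two in each section and modest extra data entry for 24 to 28 patients at one site. Treatment, visits and sample size do not change.

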8.4 Definition of a Serious Adverse Event (SAE)

An SAE is any adverse drug experience occurring at any dose that results in any of the following outcomes:

- death,
- a life-threatening event (at risk of death at the time of the event),
- requires inpatient hospitalization or prolongation of existing hospitalization,
- a persistent or significant disability/incapacity, or
- a congenital anomaly/birth defect in the offspring of a subject.

Important medical events that may not result in death, be life-threatening, or require hospitalization may be considered a serious adverse drug event when, based upon appropriate medical judgment, they may jeopardize the subject and may require medical or surgical intervention to prevent one of the outcomes listed in this definition.

A distinction should be drawn between serious and severe AEs. A severe AE is a major event of its type. A severe AE does not necessarily need to be considered serious. For example, nausea that persists for several hours may be considered severe nausea, but would not be an SAE. On

the other hand, a stroke that results in only a limited degree of disability may be considered a mild stroke, but would be an SAE.

8.4.1 Relationship of SAE to study drug or other intervention or procedure

The relationship of each SAE to the study intervention will be characterized using one of the following terms in accordance with CHOP IRB Guidelines: definitely, probably, possibly, unlikely or unrelated.

8.4.2 IRB/IEC Notification of SAEs

The IRB will be promptly notified of all on-site AEs that are (1) serious, (2) unexpected and (3) related to the research procedures. Other unanticipated problems involving risk to subjects or others will also be reported promptly using the CHOP Internal SAE reporting form and in accordance with the following timeline.

Type of Internal Adverse Event	Initial Notification (Phone, Email, Fax)	Written Report
Internal (on-site) SAEs Death or Life Threatening	24 hours	Within 2 calendar days
Internal (on-site) SAEs All other SAEs	7 days	Within 7 business days
Unanticipated Problems Related to Research	7 days	Within 7 business days
All other AEs	N/A	Summary of AEs Reported at Time of Continuing Review

8.4.3 Follow-up report

If an SAE has not resolved at the time of the initial report, a follow-up report including all relevant new or reassessed information (e.g., concomitant medication, medical history) should be submitted to the IRB. All SAE should be followed until either resolved or stable.

9. STUDY ADMINISTRATION

9.1 Data collection and management

9.1.1 Confidentiality

Demographic data including each patient's name, MRN, DOB, and a unique patient study number is entered and stored in Oncore CRM (Forte Research), the CCCR's clinical trial management system. Data regarding markers of Acute Kidney Injury (Cystatin-C, KIM-1, NGAL, NAG) will be collected using secure OnCore electronic case report forms (eCRFs). Results of standard renal function tests, audiograms, bone-specific alkaline phosphatase assays, nutritional assessments, and response assessments (radiographic and histologic) as well as toxicity data will also be entered into Oncore eCRFs. Patient related outcomes forms

Protocol number: CHP12ST051
Amendment number:
Version date: April 2, 2013

completed by a parent will be stored in a locked file cabinet in the CTRB. These forms will have patient identifiers (name, DOB, MRN).

9.1.2 Security

OnCore is maintained on a Research IS server that is password protected and backed up frequently. File cabinets in CTRB with paper forms will be kept locked.

9.1.3 Anonymization, de-identification, or destruction

The PHI in OnCore will be kept indefinitely.

9.2 Confidentiality

All data and records generated during this study will be kept confidential in accordance with CHOP Institutional policies and HIPAA on subject privacy and the Investigator and other site personnel will not use the data and records for any purpose other than conducting the study. Records with identifiers will be retained indefinitely in a secure, password protected commercial clinical trial management system (OnCore).

Safeguards to maintain subject confidentiality are described under Data Collection and Management (Section 9.1).

9.3 Regulatory and ethical considerations

9.3.1 Data safety and monitoring plan

The research team led by the protocol PI will monitor adverse events related to the protocol therapy in real time. The progress of every patient actively receiving treatment on this study will be discussed weekly in the Solid Tumor Team Meeting. An interim analysis to assess the safety of the interventions will be performed after the first 12 patients have completed therapy.

9.3.2 Risk assessment

There is risk associated with the addition of pantoprazole to cisplatin therapy, however PPIs are widely used in pediatric medicine and there is substantial experience with the toxicities associated with these agents (Section 7.1, Adverse Events). Single IV doses of pantoprazole are very well tolerated in children. An association between the use of PPIs and *C. difficile* colitis was recently reported, but the use of pantoprazole in this study is limited to 4 doses. The use of cisplatin and pantoprazole together has not been studied in children. As described in the background, we do not expect pantoprazole to alter the excretion of cisplatin. PPIs are frequently administered chronically to patients receiving chemotherapy for symptoms of reflux. The risk associated with administration of pantoprazole with cisplatin must be considered greater than minimal.

Prolonging the infusion duration may alter the toxicity profile of HDMTX because the pharmacologic effect of MTX is determined by the duration of exposure to the drug. Leucovorin rescue will start 24 h after the start of the HDMTX infusion for both infusion durations. The PK simulations (Figure 4) show that plasma concentrations at later time points are similar for the two infusion durations. There is considerable experience

Protocol number: CHP12ST051
Amendment number:
Version date: April 2, 2013

demonstrating tolerability of HDMTX in children with leukemia treated with higher doses of MTX (e.g., 33 g/m²) administered as prolonged infusions with leucovorin rescue. Administration of 12 g/m² HDMTX infused over 12 h instead of 4 h must be considered greater than minimal risk.

9.3.3 Potential benefits of trial participation

The crossover design ensures all patients will receive pantoprazole and the prolonged infusions of HDMTX. Therefore, all patients have the potential for direct benefit from participation in this study. Pantoprazole may mitigate the nephrotoxicity and hearing loss associated with cisplatin exposure. Prolonged administration of methotrexate may decrease the risk of acute kidney injury in patients receiving this agent. In addition results from this study could benefit future patients with osteosarcoma and other cancers treated with cisplatin and HDMTX if these more rational dosing methods and sensitive biomarkers of toxicity and response prove to be better.

